## 8.0 CONCOMITANT MEDICATION

All concomitant medications, both prescribed and over-the-counter, as well as dietary supplements, must be recorded in the eCRF. This includes drugs used on a chronic and as-needed basis.

### 8.1 GENERAL CONSIDERATIONS

Patients shall be advised not to start any new medication, either prescribed or over-the-counter, without consulting the Investigator, unless the new medication is required for emergency use.

[REDACTED]

[REDACTED]

[REDACTED]

[REDACTED]

[REDACTED]

[REDACTED]

[REDACTED]

[REDACTED]

### 8.3 PROHIBITED MEDICATION

The following medications and products (prescription and over-the-counter) must not be taken by the patient during the course of the study, except as noted:

- Insulin or insulin analogues, except for fixed-dose regimens that have been stable for  $\geq 4$  weeks prior to Visit 1 (Week -8 or Week -6);
- All systemic corticosteroids, except for local, topical, inhaled, or nasal corticosteroids;
- Prescription or over-the-counter agents taken for the purpose of weight reduction;
- Any non-study lipid-lowering treatments except for statins, ezetimibe, and PCSK9 inhibitors including bile acid sequestrants, fibrates, niacin ( $>100$  mg/day), omega-3 fatty acids ( $>1000$  mg/day), or any supplements used to alter lipid metabolism including but not limited to red rice yeast supplements, garlic supplements, soy isoflavone supplements, sterol/stanol products, or policosanols;
- During the 12-week Efficacy Period, dietary fiber supplements cannot be increased or started; or
- Cyclosporine, rifampin, or other inhibitors of OATP1B1 or OATP1B3 except for clarithromycin.

#### **8.4 PERMITTED MEDICATION**

The following frequently prescribed medications are permitted by the protocol, if the patient has been on a stable dose for  $\geq 4$  weeks prior to Visit 1 (Week -8 or Week -6) unless otherwise noted, and doses should remain stable throughout the duration of the study:

- Fixed-dose insulin regimens;
- Oral contraceptives and hormone replacement therapy;
- Statins, ezetimibe, or PCSK9 inhibitors that have been at a stable dose for  $\geq 6$  weeks prior to Visit 1 (Week -8 or Week -6);
  - After completion of the 12-week Efficacy Period (Visit 7 [Week 12]), patients not on statins, ezetimibe, or PCSK9 inhibitors may initiate therapy, and patients receiving statins, ezetimibe, or PCSK9 inhibitors may alter their dose; and
  - Simvastatin 80 mg or Vytorin (ezetimibe/simvastatin) 10/80 mg are permitted if tolerated for  $\geq 6$  weeks prior to Visit 1 (Week -8 or Week -6). However, simvastatin 80 mg or Vytorin 10/80 mg cannot be started at any point during the study;
- Dietary fiber supplements that are taken as part of the TLC diet during the lifestyle stabilization period may be used at a stable dose for the duration of the study. Dietary fiber supplements cannot be increased or started during the 12-week Efficacy Period;
- Chronic prescription pharmacotherapy for metabolic or CVD management or risk factor modification;
  - During the 40-week Extension Period, patients not on chronic prescription pharmacotherapy for metabolic or CVD management (other than statins, ezetimibe, or PCSK9 inhibitors) or risk factor modification may initiate therapy, and patients receiving therapy may alter their dose, as indicated by guidelines or local standard of care;
- Tamoxifen, estrogens, or progestins that have been at a stable dose for  $\geq 4$  weeks prior to the first TG qualifying visit (Visit 2 [Week -2]);
- Thyroid replacement therapy that has been at a stable dose for  $\geq 4$  weeks prior to the first TG qualifying visit (Visit 2 [Week -2]); and
- Local, topical, inhaled, or nasal corticosteroids.

Note: Other than the prohibited medications (see Section 8.3), medications needed for chronic conditions and AEs are permitted.

---

## **8.5 PATIENT RESTRICTIONS**

### **8.5.1 Therapeutic Lifestyle Changes**

The Investigator or designee will provide TLC instructions based on the NCEP recommendations (see Appendix E) with implementation beginning at Visit 1 (Week -8 or Week -6). From Visit 4 (Day 1), the Investigator or designee will instruct patients to stably maintain these lifestyle changes. Goals and recommendations on diet, weight loss, physical activity, and abstaining from alcohol will be reviewed at all study visits.

---

## **9.0 ADVERSE EVENTS**

### **9.1 ADVERSE EVENT DEFINITION**

An AE is any untoward medical occurrence in a patient administered a pharmaceutical product and which does not necessarily have a causal relationship with the pharmaceutical product. An AE can, therefore, be any unfavorable and unintended sign, symptom, or disease temporally associated with the use of a medicinal product, whether or not related to the medicinal product. Any worsening of the patient's disease under study or other medical conditions will also be considered to be an AE, unless it is within the normal range of disease fluctuation for that patient.

Clinically meaningful (for a given patient) changes in physical examination findings and abnormal objective test findings (e.g., clinical laboratory tests, ECGs) will also be recorded as AEs. The criteria for determining whether an abnormal objective test finding will be reported as an AE are as follows:

1. Test result is associated with accompanying symptoms, and/or;
2. Test result requires additional diagnostic testing or medical/surgical intervention, and/or;
3. Test result leads to a change in study drug dosing or discontinuation from the study, significant additional concomitant drug treatment or other therapy, and/or;
4. Test result leads to any of the outcomes included in the definition of an SAE.

Merely repeating a test, in the absence of any of the above conditions, does not meet condition number 2 above for reporting as an AE.

Any abnormal test result that is determined to be an error does not require reporting as an AE.

A treatment-emergent AE (TEAE) is defined as an AE that begins after the start of study drug or an event that begins before the start of the study drug and worsens in intensity after starting treatment with the study drug.

### **9.2 ADVERSE DRUG REACTIONS**

All noxious and unintended responses to a medicinal product related to any dose will be considered adverse drug reactions. The phrase "responses to a medicinal product" means that a causal relationship between a medicinal product and the AE is at least a reasonable possibility (see Section 9.3).

### **9.3 REPORTING ADVERSE EVENTS**

At each evaluation, the Investigator will determine whether any AEs have occurred. The patient will be questioned in a general way and no specific symptoms will be suggested. If any AEs have occurred, they will be recorded on the AE pages of the eCRF and in the

---

patient's medical record. If known, the diagnosis should be recorded, in preference to the listing of individual signs and symptoms.

Adverse event assessment and reporting begins with the signing of informed consent, and occurs at every scheduled study visit through Visit 11 (Week 52), unless an unresolved AE is still being followed (see Section 9.4).

The severity (intensity) of AEs will be classified as follows:

- Mild: An AE that is easily tolerated by the patient, causes minimal discomfort, and does not interfere with everyday activities;
- Moderate: An AE that causes enough discomfort to interfere with normal everyday activities and may require intervention; and
- Severe: An AE that prevents normal everyday activities;
  - Note: Treatment or intervention will usually be required.

The Investigator will make a judgment regarding whether or not the AE was related to the study drug. The following factors should be considered:

- The temporal sequence from study drug administration-
  - The event should occur after the study drug is given. The length of time from study drug exposure to event should be evaluated in the clinical context of the event.
- Underlying, concomitant, intercurrent diseases-
  - Each report should be evaluated in the context of the natural history and course of the disease being treated and any other disease the patient may have.
- Concomitant drugs-
  - The other drugs the patient is taking or the treatment the patient receives should be examined to determine whether any of them might be recognized to cause the event in question.
- Known response pattern for this class of study drug-
  - Clinical and/or preclinical data may indicate whether a particular response is likely to be a class effect.
- Exposure to physical and/or mental stresses-
  - The exposure to stress might induce adverse changes in the patient and provide a logical and better explanation for the event.
- The pharmacology and PK of the study drug-
  - The known pharmacologic properties (absorption, distribution, metabolism, and excretion) of the study drug should be considered.

---

The relationship of an AE to the administration of the study drug is to be assessed according to the following definitions:

- Definite: An AE which is consistent with the suspected type of reaction known for the drug, in line with the reasonable temporal order after treatment, and is alleviated or disappears upon discontinuation of the study drug;
- Probable: An AE which is consistent with the suspected type of reaction known for the drug, in line with the reasonable temporal order after treatment, alleviates or disappears upon discontinuation of the study drug, but could also be caused by the clinical conditions of the study patient or other factors;
- Possible: An AE which is consistent with the suspected type of reaction known for the drug, not in line with the reasonable temporal order after treatment, and could also be caused by the clinical conditions of the study patient or other factors;
- Improbable: An AE which is inconsistent with the suspected type of reaction known for the drug, not in line with the reasonable temporal order after treatment, and could also be caused by the clinical conditions of the study patient or other factors; and
- Not related: An AE which is inconsistent with the suspected type of reaction known for the drug, not in line with the reasonable temporal order from administration of the study drug, or that can be easily explained by other factors, such as underlying diseases, complication, concomitant drugs, and concurrent treatment.

If the causality assessment for an individual event is “Definite,” “Probable,” or “Possible,” the event will be considered a suspected adverse drug reaction.

The Investigator will evaluate any changes in laboratory values, make a determination as to whether or not the change is clinically important, and whether or not the changes were related to the study drug. However, even if the Investigator feels there is no relationship to the study drug, the AE or laboratory abnormality **MUST** be recorded in the eCRF.

The Investigator will record the action taken to treat the AE, if any, the action taken with study treatment, and the outcome for each AE in the eCRF according to the following:

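### Read literally, the causality definitions in protocol Section 9.3 contradict the reasonable-possibility standard in Sections 9.2 and 10.5: Possible requires poor timing, and no suspected category admits a new type of reaction

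*Protocol*

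**What the plan says.** Section 9.2 counts a response as an adverse drug reaction when "a causal relationship between a medicinal product and the AE is at least a reasonable possibility", and points to Section 9.3. Section 10.5 applies the same standard to suspected adverse reactions and also points to Section 9.3. It expects some suspected reactions to be unexpected, that is, not listed in the reference safety information. One of its examples of supporting evidence is an event not usually linked to drug exposure.

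Section 9.3 first lists factors for the Investigator to weigh. On timing it says "The length of time from study drug exposure to event should be evaluated in the clinical context of the event". It then says that relationship "is to be assessed according to the following definitions":

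- **Definite**: known reaction type, reasonable timing, and improvement on stopping the drug.
- **Probable**: the same, with the condition that the event "alleviates or disappears upon discontinuation of the study drug", plus another possible cause.
- **Possible**: "Possible: An AE which is consistent with the suspected type of reaction known for the drug, not in line with the reasonable temporal order", plus another possible cause.
- **Improbable**: identical to Possible, including the timing words, except that the reaction type is inconsistent.
- **Not related**: inconsistent type, poor timing, "or that can be easily explained by other factors, such as underlying diseases, complication, concomitant drugs, and concurrent treatment".

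If the grade is Definite, Probable or Possible, "the event will be considered a suspected adverse drug reaction".

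**The concern.** Sections 9.2 and 10.5 rely on Section 9.3 to apply their standard, but its definitions do something different in three respects.

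- **Timing.** Poor timing is a condition of Possible, whereas the factor list treats timing as something to weigh in context.
- **Reaction type.** A type known for the drug is required for every suspected category, although Section 10.5 expects suspected reactions that are not yet listed.
- **Improvement on stopping.** Definite and Probable require it. The action-taken and outcome lists in Section 9.3 allow for dosing to continue unchanged and for death from the event; in neither case can improvement on stopping be seen.

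Three uses of the investigator's grade are exposed:

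1. The AE summaries by relationship to study drug and treatment group (Section 11.6).
2. The investigator's suspected classification, which feeds SUSAR identification. Fatal SUSARs carry a 7-day limit (Section 10.5), and a well-timed fatal event is one of those that meets no suspected category.
3. Possibly, SAE reporting after the 30-day follow-up, which depends on whether the Investigator considers the event related (Section 10.6.1.1).

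**Working it through.** The plan gives no figure to reproduce, so the check is logical. Code four yes/no features from the Section 9.3 definitions:

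- K = reaction type known for the drug
- T = reasonable timing
- D = improvement on stopping
- A = another possible cause

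This gives 2^4 = 16 profiles. The definitions become:

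- Definite = K and T and D
- Probable = K and T and D and A
- Possible = K and not T and A
- Improbable = not K and not T and A
- Not related = (not K *and/or* not T), or easily explained by other factors. The punctuation does not settle which connective applies.

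**Profiles meeting a suspected category**

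- Definite or Probable: K, T and D fixed, A free, so 2 profiles, both well timed.
- Possible: K, not T and A fixed, D free, so 2 profiles, both badly timed.
- Total: 2 + 2 = 4 of 16.

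| Group | Meets a suspected category |
|---|---|
| Well timed | 2 of 8 |
| Badly timed | 2 of 8 |
| New type, any timing | 0 of 8 |
| Known type, well timed, no improvement on stopping | 0 of 2 |
| No improvement, well timed | 0 of 4 |
| No improvement, badly timed | 1 of 4 |

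**Where the other 8 − 2 = 6 well-timed profiles go.** Four are of a new type. Two are of a known type without improvement on stopping.

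| Reading of Not related | Fit Not related | Fit no category |
|---|---|---|
| *and* | 0 | 6 |
| *and*, with any other possible cause counted as easily explained | 3 | 3 |
| *or* | 4 (all new type) | 2 |
| *or*, with any other possible cause counted as easily explained | 5 | 1 |

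On the *or* reading, both Possible profiles also satisfy Not related, so the same event meets a suspected and an unsuspected category.

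**Would a smaller edit do?**

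- Reverse only the timing in Possible (K and T and A): 3 of 8 well timed and 0 of 8 badly timed are suspected. New types remain excluded.
- Also drop known type but keep another possible cause as a condition (T and A): 5 of 8 and 0 of 8. A well-timed new-type event with no other explanation is still outside, although the absence of another explanation strengthens the case for the drug.
- Define Possible by reasonable possibility: the 2 Definite/Probable profiles stay suspected by definition, and the other 14 (6 well timed, 8 badly timed) go to judgment. If Improbable and Not related are left unedited, 4, 9, 12 or 13 of those 14 would still literally meet one of them, in the order of the table above. Those two categories therefore need a matching edit.

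**The case against.** The best reply is that the definitions do not work alone. Section 9.3 asks for the Investigator's judgment on six factors first. It says that the three grades make an event suspected, not that only they can. Section 10.5 keeps its own definition and makes the Sponsor responsible for SUSAR reporting. Every SAE up to 30 days after the last dose is reportable within 24 hours whatever its cause, and AEs are recorded "even if the Investigator feels there is no relationship to the study drug". A new-type or fatal serious event therefore reaches safety review whatever its grade. This stands, and it makes the problem a conflict to reconcile, not a bar to reporting.

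A second reply is that neither Section 9.2 nor Section 10.5 sets a timing rule, so counting badly timed events as suspected is merely over-inclusive. It is true that the conflict over reaction type is the more direct one. But the inverted timing also excludes: it keeps a well-timed known-type event out of Possible when it has not improved on stopping and so cannot be Definite or Probable.

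Third, the improvement condition could be read as applying only where the drug was stopped and the outcome could be observed. That is a sensible reading, but the text does not state it.

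Finally, the profile counts do not measure impact, and the study is finished. Both points are right, and both limit what can now be done.

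**Conclusion.** The concern holds. Applied as written, Section 9.3 does not deliver the standard that Sections 9.2 and 10.5 expect from it. No suspected category admits a new type of reaction, and poor timing is a condition of Possible.

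This rests on a literal reading and on treating continued dosing or a fatal outcome as not meeting the improvement condition. The 16 profiles show the logic only; they carry no weights, and some well-timed events may properly be judged unrelated. Nothing in the documents shows that any event was misclassified, and no bias between arms is claimed.

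Efficacy, AE recording, SAE reporting to 30 days and the all-causality TEAE tables are unaffected. The point should be corrected because it touches the relationship tables and one input to SUSAR identification, but it does not threaten the trial's main conclusions.

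**What to change.** Reconcile Section 9.3 with Sections 9.2 and 10.5:

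1. Remove the reversed timing condition from Possible.
2. Make a known reaction type supportive evidence, not a requirement.
3. Do not make another possible cause a condition of Possible.
4. State that any event with a reasonable possibility of relation, judged on the listed factors, is at least Possible, even if of a new type. This should not make every well-timed event suspected automatically.
5. State that Improbable and Not related apply only when there is no reasonable possibility, and whether the elements of Not related are joined by *and* or *or*.

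The SAP document (Section 1) records database lock on August 23, 2019, unblinding on August 26 and a corrected lock on September 11. Rewording cannot change grades already assigned. For this trial, the study report should caveat the tables by relationship and rely on the all-causality TEAE tables.

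The cost is wording and one caveat, with no extra procedures. Wherever the revised wording is used to grade events, some more well-timed events may be classed as related and some badly timed ones no longer would be.

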#### **Action taken to treat the AE**

- None,
- Treatment required,
- Hospitalization,
- Patient withdrawn, or
- Other (specify).

### **Action taken with study treatment**

- Dose not changed,
- Drug interrupted,
- Drug withdrawn,
- Not applicable, or
- Unknown.

### **Outcome**

- Resolved: The event has recovered;
  - Note: An SAE/AE stop date should be provided.
- Resolved with sequelae: The study patient has recovered as much as may be expected but is left with sequelae of the event that are not expected to recover further;
  - Note: If the sequelae are severe enough to represent a significant disability or incapacity then the event should be reported as an SAE.
- Resolving: Can be used in cases where study patient is known to be clearly recovering from the event at the end of a study, although the event is not yet resolved, and the Investigator and Medical Monitor agree that further follow-up is not necessary;
- Death: The study patient died as a result of the AE;
  - Note: Death is considered an outcome of an AE rather than an AE in its own right, and the cause of death should be recorded as the AE. There may be rare circumstances where the cause of death is unknown and the death may have to be recorded as the event (e.g., “sudden cardiac death”). Adverse events resulting in death are SAEs.
- Not resolved: The patient has an AE that has not improved or recuperated at the time of the report; or
  - Note: The decision not to continue follow-up should be discussed between the Investigator and Medical Monitor and recorded in the source documents.
- Unknown: The outcome of the event is genuinely unknown in spite of efforts to contact the patient.

### **9.4 FOLLOW-UP OF ADVERSE EVENTS**

If any AEs are present when a patient completes the study, or if a patient is withdrawn from the study, the patient will be re-evaluated. At the Investigator's discretion, clinically minor AEs can be re-evaluated via telephone and documented. If the AE is still not resolved, additional follow-up will be performed as appropriate. Every effort will be made by the Investigator or delegate to contact the patient until the AE is resolved or stabilized, or until

---

the Medical Monitor and Investigator agree that further follow-up is not necessary. The follow-up of AEs will be documented in the patient's study records.

## **10.0 SERIOUS ADVERSE EVENTS**

An SAE is any untoward medical occurrence that at any dose:

- Results in death,
- Is life-threatening,
- Requires patient hospitalization or prolongation of existing hospitalization,
- Results in persistent or significant disability/incapacity,
- Is a congenital anomaly/birth defect, or
- Is an important medical event.

Medical and scientific judgment should be exercised in deciding whether reporting is appropriate in other situations, such as important medical events that may not be immediately life-threatening or result in death or hospitalization but may jeopardize the patient or may require intervention to prevent one of the other outcomes listed in the definition above.

### **10.1 LIFE-THREATENING ADVERSE EVENT**

The term “life-threatening” in the definition of “serious” refers to an event in which the patient was at risk of death at the time of the event. It does not refer to an event which hypothetically might have caused death if it were more severe.

### **10.2 HOSPITALIZATION OR PROLONGATION OF EXISTING HOSPITALIZATION**

Hospitalization is defined as the patient being hospitalized overnight, or the patient's hospital stay being prolonged for at least an additional overnight stay. An emergency room visit without hospital admission will not be recorded as an SAE under this criterion, nor will hospitalization for a procedure scheduled or planned before the signing of informed consent. However, unexpected complications and/or prolongation of hospitalization that occur during elective surgery should be recorded as AEs and assessed for seriousness. Admission to the hospital for social or situational reasons (i.e., no place to stay, live too far away to come for hospital visits) will not be considered inpatient hospitalizations. Twenty-three hour hospitalizations for observation should be discussed with the Medical Monitor to determine whether they are appropriate for SAE reporting.

